11.4 Methods for Evaluation of Disease

All measurements should be taken and recorded in metric notation using a ruler, calipers, or a digital measurement tool. All baseline evaluations should be performed as closely as possible to the beginning of treatment and never more than 4 weeks before the beginning of the treatment.

The same method of assessment and the same technique should be used to characterize each identified and reported lesion at baseline and during follow-up. Imaging-based evaluation is preferred to evaluation by clinical examination unless the lesion(s) being followed cannot be imaged but are assessable by clinical exam.

11.5 Evaluation of Best Response

The best overall response is the best response recorded from the start of the treatment until disease progression (taking as reference for progressive disease the smallest measurements recorded since the treatment started). If a response recorded at one scheduled MRI does not persist at the next regular scheduled MRI, the response will still be recorded based on the prior scan, but will be designated as a non-sustained response. If the response is sustained, i.e. still present on the subsequent MRI at least four weeks later, it will be recorded as a sustained response, lasting until the time of tumor progression. Participants without measurable disease may only achieve SD or PD as their best “response.”

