5.3 Treatment and Evaluation Cycles

At the beginning of each treatment cycle (i.e., every 3 weeks) patients will also have safety laboratory studies, physical examination, assessment of KPS, and complete the MDASI questionnaire. During discussion of the patient's progress, adverse events and concomitant medications will be collected by targeted questioning.

Patients who remain on study will have tumor response assessments performed at 8 weeks (± 7 days) after initiation of therapy and then every 8 weeks (± 7 days) thereafter.

In addition to reassessment scans, confirmatory scans should also be obtained not less than 4 weeks following initial documentation of objective response (OR). To be assigned a status of PR or CR, changes in tumor measurements must be confirmed by repeat assessments that should be performed no less than 4 weeks after the criteria for response are first met.

Patients are to return to the clinic every 3 weeks during the first 6 months on trial. If after 6 months, the patient and the investigator may agree to extend the interval for clinic visits to every 9 weeks (3 cycles). The laboratory assessments must still be performed every three weeks but may be done locally. Brain MRI or CT (for patients who cannot receive MRI scans) will be repeated every 8 weeks, with a 10-day window is allowed after the first 6 cycles.

Unscheduled visits: If a brain surgery or biopsy is scheduled during the active study or within 30 days from the end of treatment date, the investigator may obtain tumor tissue with patient's consent.

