11. MEASUREMENT OF EFFECT

After signing informed consent patients will undergo screening procedures including baseline radiologic imaging by contrast-enhanced CT scan or MRI within 14 days prior to initiating study drugs.

Patients who remain on study will have tumor assessments performed at 8 weeks (± 1 week) after initiation of therapy and then every 8 weeks (± 1 week) thereafter. In addition to reassessment scans, confirmatory scans should also be obtained not less than 4 weeks following initial documentation of objective response. To be assigned a status of PR or CR changes in tumor measurements must be confirmed by repeat assessments that should be performed no less than 4 weeks after the criteria for response are first met.

Efficacy will be assessed by the RANO response criteria as noted below. RANO-HGG and RANO-LGG will be used for each evaluation to assess contrast-enhancing lesions and T2/FLAIR hyper-intense lesions, respectively.

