11.1 Definitions

Evaluable for Efficacy and Safety

Patients who have received at least one dose of study drug will be considered evaluable for efficacy and safety. These patients will have response classified according to the definitions stated below.

Evaluable for Intratumoral Concentrations

Patients in Arms C and E must have sufficient tumor tissue from biopsy to permit quantitation of intratumoral concentrations of ONC201 to be considered evaluable for these arms. Patients found to have insufficient tissue may continue treatment, but will be replaced.

Evaluable Non-Target Disease Response

Patients who have lesions present at baseline that are evaluable but do not meet the definitions of measurable disease ($a+b > 10\text{mm}$), have received at least one cycle of therapy, and have had their disease re-evaluated will be considered evaluable for nontarget disease. The response assessment is based on the presence, absence, or unequivocal progression of the lesions.

Disease Parameters

For the purposes of this study, patients should be reevaluated for response at 8 weeks of therapy and then every 8 weeks thereafter. In addition to baseline scan(s), confirmatory scans should also be obtained not less than 4 weeks following initial documentation of objective response.

ORR by RANO-HGG is defined as the proportion of subjects in the analysis population who have confirmed complete response (CR) or partial response (PR) using RANO-HGG criteria. Radiographic assessments will be performed by the investigator for the primary endpoint, but may also be separately assessed by blinded independent central review. Duration of response

is defined as time from first RANO-HGG response (only if confirmed) to disease progression in subjects who achieve a PR or better.

ORR by RANO-LGG is defined as the proportion of subjects in the analysis population who have confirmed CR, PR, or minor response (MR) using RANO-LGG criteria determined by the investigator (but may be separately assessed by blinded independent central review). Duration of response is defined as time from first RANO-LGG response (only if confirmed) to disease progression in subjects who achieve a MR or better.

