11.3 Response/Progression Categories

The modified RANO Response Criteria to be used in this study are summarized below. If changes in the primary field lesions lead to assessment of progressive disease, this assessment must be confirmed at least 4 weeks later.

11.3.1 Complete response (CR). All of the following criteria must be met:

- a) Complete disappearance of all enhancing measurable and non-measurable disease sustained for at least 4 weeks. In the absence of a confirming scan at least 4 weeks later, this scan will be considered only stable disease.
- b) No new lesions.
- c) All measurable and non-measurable lesions must be assessed using the same techniques as baseline.
- d) Participants must be on no steroids or on physiologic replacement doses only.
- e) Stable or improved non-enhancing (T2/FLAIR) lesions.
- f) Stable or improved clinically, for clinical signs and symptoms present at baseline and recorded to be disease related.

Participants with non-measurable disease cannot have a complete response. The best response possible is stable disease.

11.3.2 Partial response (PR). All of the following criteria must be met:

- a) Greater than or equal to 50% decrease compared to baseline in the sum of products of perpendicular diameters of all measurable enhancing lesions sustained for at least 4 weeks. In the absence of a confirming scan at least 4 weeks later, this scan will be considered only stable disease.
- b) No progression of non-measurable disease.
- c) No new lesions.
- d) All measurable and non-measurable lesions must be assessed using the same techniques as baseline.
- e) The steroid dose at the time of the scan evaluation should be no greater than the dose at time of baseline scan.
- f) Stable or improved non-enhancing (T2/FLAIR) lesions on same or lower dose of corticosteroids compared to baseline scan.
- g) Stable or improved, for clinical signs and symptoms present at baseline and recorded to be disease related clinically.

Participants with non-measurable disease cannot have a partial response. The best response possible is stable disease.

11.3.3 Progressive disease (PD).

Any of the following criterion must be met:

- a) > 25% increase in sum of the products of perpendicular diameters of enhancing lesions (over best response or baseline if no decrease) on stable or increasing doses of corticosteroids.
- b) Any new enhancing measurable lesion.

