The primary efficacy endpoint is PFS-6, defined as the proportion of subjects in the analysis population who remain progression-free for at least six months following initiation of study therapy. Response for the primary analysis will be determined by the investigator assessment, and a confirmation assessment is required per RANO. If patients discontinue protocol therapy at or before 6 months without tumor imaging performed, the patient will be treated in the primary endpoint analysis as a treatment failure. Adjustments will not be made for multiple comparisons.

Secondary efficacy endpoints include: (1) ORR defined as the proportion of subjects in the analysis population who have complete response (CR) or partial response (PR) using RANO criteria; (2) duration of response, defined as time from first RANO response to disease progression in subjects who achieve a PR or better; (3) progression-free survival (PFS), defined as the time from initiation of study therapy to the first documented disease progression according to RANO or death due to any cause, whichever occurs first; and (4) overall survival (OS).

Additional supportive analyses of duration of response and PFS will be conducted using RANO criteria, in which a confirmation assessment of disease progression must be obtained at least 4 weeks after the initial disease assessment indicating progressive disease.

Safety will be assessed by quantifying the toxicities and grades experienced by subjects who have received ONC201, including serious adverse events (SAEs). Other safety endpoints include laboratory safety assessments, KPS status, and vital signs.

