#### 3. Analyses

All analyses will be presented by Arm and for All Patients. Otherwise, specified patient disposition, study drug usage, prior/concomitant/post-ONC201 medications, demographic and baseline characteristics, adverse events, and laboratories will use methods and summaries defined in the ISS SAP.

Laboratory boxplots will be presented for all tests with at least 60 patients having numeric baseline results: one plot per test, time on the x-axis, value on the y-axis. The plots will not be broken out by arm (i.e. only the All Patients group). Only Baseline and Cycles 2-12 will be presented. For Cycles 2-12, nominal visits will be used; if multiple values are associated with a visit, the highest value will be used for chemistry tests and lowest value will be used for hematology tests.

The following efficacy analyses will be performed: best overall response, overall response rate, disease control rate, duration of response, progression-free survival, and overall survival. All analyses will be

based on the investigator-assessed overall RANO response. Discontinuation of treatment due to progressive disease will also be considered. All analyses, aside from overall survival, will be censored at the earlier of: (1) last disease assessment or (2) initiation of other anticancer therapy.

Cycle 1, 2 hour ONC201 plasma concentrations will be summarized descriptively.

Collected data contributing to presented tables and figures will be listed.

Other analyses specified in the protocol will either not be completed, or will be defined outside the scope of this plan.

Following is a complete list of the tables, figures, and listings to be prepared (with clarifying notes in parentheses).

Number	Description
Table 1.1	Patient Disposition
Table 1.2	Demographics and Baseline Characteristics
Table 1.3	Study Drug Usage
Table 1.4.1	Prior Medications
Table 1.4.2	Concomitant Medications
Table 1.4.3	Post-ONC201 Medications
Table/Figure 2.1	Progression-free Survival
Table/Figure 2.2	Overall Survival
Table 2.3	Response Rate (includes ORR, BOR, and DCR)
Table/Figure 2.4	Duration of Response
Table 3.x.1*	Treatment-emergent Adverse Events (TEAE)
Table 3.x.2*	TEAE Grade 3 and Above
Table 3.x.3*	Serious TEAE
Table 3.x.4*	TEAE Leading to Death
Table 3.x.5*	TEAE Leading to Study Drug Discontinuation, Reduction, or Interruption
Table 3.x.6*	Study Drug Related TEAE
Table 3.x.7*	Study Drug Related TEAE Grade 3 and Above
Table 3.x.8*	Study Drug Related Serious TEAE

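### Section 11.5 keeps non-persisting responses as recorded responses, against the confirmation rule elsewhere in the protocol; best overall response, the derivation of ORR and the futility rule for Arms B, D and F need one stated rule

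*Protocol*

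**What the plan says.** **Confirmation is required in four places.** Protocol 5.3 makes it a condition of CR or PR status: "changes in tumor measurements must be confirmed by repeat assessments that should be performed no less than 4 weeks after" the criteria are first met. The opening of section 11 repeats this: "To be assigned a status of PR or CR changes in tumor measurements must be confirmed by repeat assessments". Section 11.1 defines ORR by RANO-HGG as the proportion "who have confirmed complete response (CR) or partial response (PR) using RANO-HGG criteria". It does the same for RANO-LGG, and it counts duration of response only for confirmed responses. Sections 11.3.1 and 11.3.2 say what happens otherwise: "In the absence of a confirming scan at least 4 weeks later, this scan will be considered only stable disease".

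**Section 11.5 says something else.** "The best overall response is the best response recorded from the start of the treatment until disease progression". If the response has gone by the next scheduled MRI, "the response will still be recorded based on the prior scan, but will be designated as a non-sustained response".

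**The analysis text does not choose between them.** Section 13.1 defines ORR as the proportion of subjects "who have complete response (CR) or partial response (PR) using RANO criteria", and neither ORR nor duration of response carries the word confirmed there. Section 13.1 does ask for a confirmation assessment, but in a sentence about the primary analysis, which is PFS-6. SAP section 3 says that its efficacy analyses are "based on the investigator-assessed overall RANO response" and does not mention confirmation. Table 2.3 reports ORR, best overall response and disease control rate.

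**Futility.** Protocol 13.2 ends accrual in Arm B, D or F when the first 16 evaluable patients include no objective response and at most 7 are progression-free over the first 2 months. It does not say whether the response must be confirmed.

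**The concern.** A CR or PR seen on one scan and not on the next is stable disease under 11.3 and a recorded response under 11.5. Two programmers working from the same data could produce different best-response tables, each with a section of the protocol to cite. Best overall response is the most exposed, because 11.5 is the section that defines it. ORR is exposed at one remove, through a table built on recorded investigator responses.

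The same uncertainty reaches a decision rule. In Arms B, D and F the two futility conditions are joined, so a single response that counts keeps the arm accruing however poor PFS-2 is. With 16 to 30 patients per arm, that is up to 30 − 16 = 14 further patients.

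**Working it through.** **1. The texts side by side.** Take a patient with a PR at week 8, no extra scan at week 12, and no PR at week 16.

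- 5.3, 11 and 11.3.2: not a PR; stable disease.
- 11.1: not in ORR, and no duration of response.
- 11.5: PR recorded from the week-8 scan and labelled non-sustained; best overall response is PR.
- 13.1 and the SAP: no explicit instruction.

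The label non-sustained does not always mean unconfirmed. A PR confirmed by an extra scan at week 12 and lost by week 16 is confirmed but did not persist at the next scheduled MRI. However, 11.5 goes on to describe a sustained response as one still present on a later MRI at least four weeks on, which is in substance the confirmation test. So its non-sustained group includes unconfirmed responses.

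**2. Effect on a rate.** One extra response shifts ORR, or the CR/PR share of best overall response, by 1/n: 1/30 = 3.3 points, or 1/16 = 6.3 points. Arms B, D and F plan 16 to 30 patients. Protocol 13.3 leaves participants without measurable disease out of ORR, so n may be smaller and the shift larger.

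**3. Timing at the futility look.** The first scan is at day 56 ± 7 and confirmation comes at least 28 days later: nominally day 56 + 28 = 84 (week 12), at the earliest day 49 + 28 = 77. Two months is about 61 days. A response first seen at the week-8 scan therefore cannot be confirmed at that patient's 2-month point. Patients enrolled early among the 16 may already have a confirming scan by the calendar date of the look; the latest ones will not.

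**4. The plan's own stopping probabilities.** Let X be the number progression-free at 2 months out of 16, binomial with rate p.

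- P(X ≤ 7 | p = 0.44) = 0.595; 13.2 states 0.6.
- P(X ≤ 7 | p = 0.67) = 0.047; 13.2 states 0.046.

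Both reproduce. They use PFS-2 alone and are the same figures as for Arm A, so for Arms B, D and F they leave out the response condition.

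**5. Adding the response condition.** Let q be the rate of responses that count, with responders a subset of patients progression-free at 2 months:

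P(stop) = Σ (k = 0 to 7) C(16,k) (p − q)^k (1 − p)^(16−k).

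If response is instead independent of PFS-2, P(stop) = P(X ≤ 7)(1 − q)^16. The chance of at least one countable response is 1 − (1 − q)^16. The documents give no value for q, so a range is assumed.

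| Assumed q | P(at least one in 16) | P(stop), p = 0.44, subset | P(stop), p = 0.44, independent | P(stop), p = 0.67, subset |
|---|---|---|---|---|
| 0% | 0 | 0.595 | 0.595 | 0.047 |
| 2% | 0.276 | 0.457 | 0.431 | 0.038 |
| 5% | 0.560 | 0.302 | 0.262 | 0.028 |
| 10% | 0.815 | 0.144 | 0.110 | 0.016 |

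If 2% of patients have a confirmed response and a further 3% an unconfirmed one, counting both rather than the confirmed ones alone lowers the null stopping probability from 0.457 to 0.302.

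The null PFS-2 rate is a separate matter. Under the stated exponential assumption, 0.1^(1/3) = 0.464 rather than 0.44. With 0.464 the subset values at q = 0, 2% and 5% are 0.517, 0.400 and 0.267, so the pattern is the same.

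**The case against.** The strongest reply is that the protocol has already decided the matter. Section 11.1 is the explicit definition of ORR, and it requires confirmation under both RANO versions. Sections 5.3 and 11 withhold CR or PR status until confirmation. Section 13.1 counts CR and PR by RANO criteria, and the criteria for this study are those in 11.3, so its shorter wording can be read as carrying confirmation with it.

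This stands, and it limits the point. A reader might infer that the plan as written counts unconfirmed responses in ORR and starts the duration-of-response clock for them. The documents do not support that: 11.1 excludes both, and the result follows only if 11.5 or the bare wording of 13.1 is used in its place. Nor does the SAP permit unconfirmed responses. It is silent, calls itself abbreviated, and refers to an integrated efficacy SAP that is not among the documents. An argument from steroid changes would also be weak, because the CR and PR criteria already restrict steroid dose.

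The reply does not remove the conflict over best overall response. Section 11.5 defines that endpoint and gives a different result from 11.3 for the same scans. It also does not reach 13.2, where nothing says which kind of response prevents stopping. Requiring a confirmed response there without more would not work either, because the confirming scan falls after the 2-month point.

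**Conclusion.** The point holds in three parts of different strength.

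- **Best overall response:** a direct contradiction between 11.5 and 11.3. Following 11.5 counts unconfirmed CR and PR in Table 2.3.
- **ORR and duration of response:** the protocol's definition is confirmed response. The weakness is that 13.1 and the SAP do not repeat it, so a table built from recorded responses could depart from 11.1.
- **Futility in Arms B, D and F:** a real gap. The status of an unconfirmed response is not stated, and one countable response is enough to block stopping.

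The sizes are illustrative. The shift of 3.3 points (n = 30) or 6.3 points (n = 16) is per unconfirmed response, and nothing in the documents says how many to expect. The fall in stopping probability from 0.457 to 0.302 rests on assumed countable response rates of 2% and 5%, PFS-2 of 0.44, and responders being among those progression-free at 2 months. No figure stated in the plan depends on confirmation of response, and the PFS-6 test is not affected. This should be corrected, but it does not undermine the primary analysis.

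**What to change.** - **Protocol 11.5:** state that a CR or PR not confirmed at least 4 weeks later is stable disease for best overall response. Show unconfirmed and non-sustained responses on a separate line, and keep the two labels distinct.
- **Protocol 13.1 and SAP section 3 (Tables 2.3 and 2.4):** add the condition that responses are confirmed to ORR and duration of response, to match 11.1.
- **Protocol 13.2, Arms B, D and F:** say how a response first seen at week 8 and not yet confirmed is handled at the look. One workable rule is that the accrual decision for that arm waits for the scan at least 4 weeks later, and only a confirmed response prevents stopping.

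The cost is wording and one derived variable. ORR and the CR/PR share of best overall response may come out slightly lower. The futility decision may be delayed by about 4 weeks, but only when a pending response would decide it.

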12. DATA REPORTING / REGULATORY REQUIREMENTS

Adverse event lists, guidelines, and instructions for reporting adverse events can be found in Section 7.

12.1 Data Reporting

Investigative sites are responsible for completing and submitting data and/or data forms according to the user requirements of the EDC system.

12.2 Data Collection

12.2.1 Data Collection Forms

Qualified clinical trial study monitors that represent the Sponsor will complete onsite (or remote) monitoring. The Sponsor will be responsible for all data management and statistical analysis.

Case Report Forms will be completed in a timely manner. Case Report Form completion may be formally delegated to other study personnel listed in the delegation of authority (DOA) form and signed by the PI.

The following steps will be taken to ensure accurate, consistent, complete, and reliable data:

1. The Sponsor or designee will conduct an initiation meeting at the study site prior to the start of the study. The study protocol, procedures and CRFs will be reviewed in detail and the study personnel will be trained to carry out the procedures defined in the protocol.
2. The Investigator will be provided with a Study Site Binder for storing study related regulatory and study site documentation; e.g., study logs and forms.
3. All written study documentation entries must be made in blue or black ink. The investigator must review all entries for completeness and accuracy. When changes or corrections are made on any study documentation, the person making the change must draw a single line through the error, then initial and date the correction.
4. Periodic monitoring visits will be conducted on a regular basis by the Sponsor or designee in order to verify the accuracy of data entered on each CRF against the raw data from source documents at the site. Items needing correction/clarification will be identified and brought to the attention of the study site personnel and Principal Investigator, and corrections will be made as appropriate.
5. The CRF will then be sent to the Sponsor or designee for final review and data management. The study database will be validated using appropriate validation processes.
6. The Sponsor or designee may perform a regulatory audit of the study site, and may include a complete review of the overall study conduct, regulatory documentation, and selected subject CRFs and source documents.

